6. MILESTONES

Deliverable	Estimated Timeline
Registration in the EU PAS Register	TBD
Start of data collection (estimated)	31-May-2021 [^]
Date of first annual report (estimated)	31-July-2021
Date of second annual report (estimated)	31-July-2022
Date of third annual report (estimated)	31-July-2023
End of data collection (estimated)	31-July-2023 [#]
Final report (estimated)	31 December 2023 ^x

[^] Start of data collection is the planned date for starting data extraction for the purposes of the first annual report.

[#] End of data collection is the planned date on which the analytical dataset will be first completely available; the analytic dataset is the minimum set of data required to perform the statistical analysis for the primary objective(s).

^x Final report must be prepared within 11 months of end of data collection.

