9.4. Data Sources

BSRBR is the source of core baseline data, including patient demographics and disease characteristics collected by the recruiting clinician, using a standardised form.

Follow up

BSRBR data are the source of information on anti-rheumatic treatment, updated every 6-12 months depending on how long a patient has been in the register (6 monthly for the first 3 years and 12 monthly thereafter). This change is to reduce the burden of data capture on study sites, but the same data are collected at each follow-up. As many patients starting Ruxience will have been enrolled previously when they started Mabthera, follow-up may only be every 12 months. Some patients starting Ruxience as their first anti-B cell therapy will provide data more often as per the BSRBR protocol and some trusts may decide themselves to reconsent patients each time they switch drugs and send data every 6 months for 3 years again. Data captured includes continuation on drug and dates and reasons for stopping, with details of any change in dose and commencement of any new co therapy. Clinical information to permit calculation of the Disease Activity Score in 28 joints (DAS-28) is also collected.

Endpoints

BSRBR data include reports of serious morbidity reported directly by the rheumatology team at each scheduled follow-up date. For serious events additional data are captured, either against a pre-specified set of questions for certain events of special interest or using an open request for additional data. All events included in this protocol are considered events of special interest. All serious morbidities reported to BSRBR are coded by a trained nurse using the Medical Dictionary for Regulatory Activities (MedDRA).

BSRBR is linked to the UK national death and cancer registers which allow the “flagging” of individuals such that if they die or are entered in a cancer register, the BSRBR-RA learns of the event and obtains death certificate details or cancer register details. These data are held in a separate secure data safe haven at the University of Manchester. On average deaths are usually reported within 1 week to the national register although cancers can take much longer due to the structure of national reporting. BSRBR-RA received a download of death and cancer on average once/year.

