9.7. Data Analysis

All statistical analyses will be performed by BSRBR using Stata. The annual analyses will include all patients who have received Ruxience (baseline characteristics) and event incidence reports will include all patients with study follow-up data.

Analyses will be undertaken at 12 monthly intervals and will include recruitment details, baseline characteristics and crude event rates.

The final analysis will provide the incidence rates of safety events of interest overall. If sample size allows, additional analysis in subgroups by gender and new users versus switcher from originator will be undertaken.

The general analytic approach will be descriptive and include rates of events of interest among Ruxience-treated patients. Data will be presented as number of events, incidence rates and 95 % confidence intervals. Such analyses will be performed by and at the direction of BSRBR based on an a priori statistical analysis plan (SAP) maintained by University of Manchester and shared with the Sponsor. The codes will be harmonised with other registers conducting similar analysis. A draft set of MedDRA codes is included in:

Index Date

The Index Date is the date of Ruxience initiation. Patients who switch from another therapy to Ruxience while they are enrolled in BSRBR-RA are eligible for enrollment, and the index date will be the date of Ruxience initiation.

Risk Window

Patients will be evaluated for safety events of interest while exposed to Ruxience and accrue person-time from Index Date until the first occurrence of the event of interest, death, date of last scheduled clinical data provision to the register, lost to follow up, exit from the register or completion of 3 years of follow up. The final report will censor all patients at 3 years after Date of Study Start. Follow up will be uniquely determined for each safety endpoint of interest.

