Some outcomes of interest in this study are thought to potentially occur at a higher rate while on the drug, but that increased risk subsides after the drug is discontinued (ie, serious infections, CV events). In these situations, these events will be calculated using a risk window from Ruxience initiation until 270 days (eg, 9 months) after last infusion based on Ruxience's half-life and mechanism of action. This does not apply to patients who were lost to follow-up, have exited the registry, completed 3 years of follow-up or for whom the most recent date of clinical data provision to the register is within the 270 day window, in which case data will be censored on that date instead. Based on The National Institute for Care and Health Excellence (NICE) guidelines on the use of rituximab treatment, most patients will not be considered for further treatment with Ruxience until at least 6 months from the date of last infusion.

For non-melanoma skin cancer (NMSC) and other malignancies, the manifestation of which is expected to be delayed relative to the time of exposure, the outcomes will be evaluated from drug initiation until the first event, loss to follow up or completion of 3 years of follow up, reflecting a once exposed always at risk paradigm.

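### The malignancy and NMSC risk window is not reconciled with the general stopping rule, and neither rule ends person-time where the linked cancer-register data cease to be complete

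*Protocol*

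**What the plan says.** Protocol Section 9.7 (Risk Window) first gives a general rule for the safety events of interest. Person-time runs from the index date, while the patient is exposed, to the first event or to whichever of these other stops comes earlier: "death, date of last scheduled clinical data provision to the register, lost to follow up, exit from the register or completion of 3 years". In addition, everyone is censored 3 years after Study Start in the final report, and follow-up is to be set separately for each endpoint.

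For NMSC and other malignancies the same section then gives a different list: "the outcomes will be evaluated from drug initiation until the first event, loss to follow up or completion of 3 years of follow up". The stated reason is that any patient once treated is regarded as at risk from then on. Death, register exit and last scheduled data provision are not on this list.

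On the data behind these endpoints, Section 9.4 says that "cancers can take much longer due to the structure of national reporting". It adds, on the linkage, that "BSRBR-RA received a download of death and cancer on average once/year". Rheumatology teams also report serious events at each scheduled follow-up. Section 12 bases the final report on linked register data through 3 years. Section 6 puts the complete analytical dataset at 31 July 2023 and the final report at 31 December 2023.

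**The concern.** There are two separate problems.

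1. **Two lists, no stated relation.** The malignancy sentence may only lift the exposure limit, with the general stops still in force, or it may replace them. A programmer could defend either reading, and the two give different denominators.

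2. **No stop at register completeness.** The nearest stop in the general list is the last scheduled clinical data provision. That is a clinic date and says nothing about how far the cancer-register download reaches. Time after the completeness date adds to the denominator, while a cancer that only the register would reveal cannot yet be counted.

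If such time is counted, the error lowers the rate. Malignancy is an important potential risk in the risk management plan. The study has no control group (Section 9.9) in which the same shortfall could cancel out. Section 12 foresees using the data in regulatory communications or for context. Section 9.9 mentions missed clinic reports and cancer latency as limitations, but not registration delay.

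**Working it through.** **The plan's own figures.** The protocol states no person-time cancer rate. Its only cancer figures are the proportions in Table 1. Exact (Clopper-Pearson) limits reproduce them: 1/73 = 0.0137 (0.0003 to 0.0740) for malignancy excluding NMSC, and 0/73 (0 to 0.0493) for NMSC. They are proportions, so this point does not change them.

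**The two lists side by side (Section 9.7).**

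| Stop | General rule | Malignancy/NMSC sentence |
|---|---|---|
| First event | yes | yes |
| Death | yes | not listed |
| Last scheduled data provision | yes | not listed |
| Loss to follow-up | yes | yes |
| Register exit | yes | not listed |
| 3 years | yes | yes |
| Cancer-register completeness date | no | no |

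**Timeline.** Ruxience was approved on 1 April 2020 (Sections 4 and 7). Unless a registered patient received it earlier, Study Start is no earlier than that, so the 3-year window closes no earlier than 1 April 2023. The dataset is due on 31 July 2023, at most 4 months later. If Study Start fell after 31 July 2020, the window closes after the dataset date.

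**Death, if the shorter list replaces the general one.** Assume entry uniform over the 3 years, so possible follow-up T is uniform on 0 to 3 with mean 1.5 years, and constant mortality m (not given; assumed 1 to 5 per 100 person-years). Mean time alive is the mean of (1 − exp(−mT))/m, which equals 1/m − (1 − exp(−3m))/(3m²).

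- m = 0.01: 1.485 years; 1.5/1.485 gives 1.0% too much person-time.
- m = 0.02: 1.470 years; 2.0%.
- m = 0.03: 1.456 years; 3.0%.
- m = 0.05: 1.428 years; 5.1%.

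**Register lag, on either reading.** Let L be the gap between the date to which the download is complete and the close of the window. The documents do not give it; 3, 6 and 12 months are assumed. With uniform entry and time counted to the end of the window, mean person-time is 3²/6 = 1.5 years and mean covered time is (3 − L)²/6. The uncovered share is 1 − ((3 − L)/3)².

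- L = 0.25: 1 − (2.75/3)² = 16%.
- L = 0.5: 1 − (2.5/3)² = 31%.
- L = 1: 1 − (2/3)² = 56%.

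If everyone entered at Study Start, the share would be L/3: 8%, 17% and 33%. Entry weighted towards the end would push it above the uniform-entry figures.

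If the general list governs, time also stops at the last scheduled clinic return. Let V be the gap from that return to the close of the window, uniform on 0 to d, with d = 0.5 or 1 year (the 6- and 12-monthly schedules in Section 9.4). Counted time is the mean of (3 − V)²/6, and covered time is the mean of (3 − max(V, L))²/6. For example, with d = 0.5 and L = 0.5 the mean of (3 − V)² is 7.583 and the covered value is 6.25, so 1 − 6.25/7.583 = 18% is uncovered. Across both schedules the shares are 3-5%, 11-18% and 37-47% for lags of 3, 6 and 12 months.

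**From share to bias.** If a fraction f of cancers is known only through the register, and the rest are reported by clinics in time, a constant cancer rate is understated by about f times the uncovered share. The shares above are the case f = 1. The documents give no value for f.

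**The case against.** **Death and exit.** A reader might infer that the plan instructs counting time after death or withdrawal. The documents do not support that. The general rule stops at both for the safety events of interest and makes no exception for cancer. The stated purpose of the malignancy sentence is to lift the exposure limit. The 270-day rule just before it also leaves out death, which suggests that these lists abbreviate the general one. Against this, the 270-day rule does restate exit and last data provision, the general rule is framed around exposed time, and follow-up is said to be set per endpoint. What stands is an unreconciled difference, not an instruction.

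**Time after exit.** This is not shown to be unobservable. Section 9.4 describes national flagging for death and cancer and does not say that it ends at exit.

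**Other sources.** Rheumatology teams report cancers at scheduled follow-up, and hospitals and patients report too (Sections 9.4 and 9.8). Section 9.9 rates missed serious events as improbable. This stands and makes the percentages register-only bounds. It does not close the gap, since Section 9.4 expects many patients who start Ruxience to be followed only every 12 months.

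**A later download.** "Final report must be prepared within 11 months of end of data collection" might suggest that the download can simply wait. Eleven months from 31 July 2023 is 30 June 2024, but that is a deadline for the finished report, counted from a complete dataset. It is not a feasible download date.

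**SAP.** The SAP is not shown and may set a completeness cut. The point is confined to what the protocol itself fixes, which is a cancer window stated stop by stop that leaves out the one stop its own data description calls for.

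**Conclusion.** The concern holds in a limited form. The two stopping lists in Section 9.7 conflict as written. If the shorter one were applied alone, person-time would be about 1-5% too large at the assumed mortality. On either reading, cancer person-time is not ended where register data are complete, and the dates in the protocol leave at most about 4 months between the close of the window and the dataset. The bias, where it occurs, is downward.

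Its size cannot be fixed from the documents. The figures of 16%, 31% and 56% are upper bounds for assumed lags of 3, 6 and 12 months. They rest on uniform entry, the register as sole source and time counted to the end of the window. They shrink if the clinic-return stop applies and to the extent that clinics report cancers. No figure stated in the protocol changes.

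**What to change.** State in Section 9.7, and match in the SAP, that malignancy and NMSC person-time ends at the earliest of:

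- first event;
- death;
- loss to follow-up;
- 3 years after Study Start;
- the completeness date of the cancer-register download used.

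Add register exit only if national flagging stops at exit, and say which is the case. Apply the same end date to the numerator, so that cancers dated after it are listed but not counted in the rate. Give the completeness date in the final report, and show clinic-reported and register-identified cancers separately so that the contribution of each source can be seen.

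The cost is one sentence in each document, fewer malignancy person-years and a wider confidence interval.

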9.8. Quality Control

BSRBR-RA have guidelines in place to monitor and maintain the quality of the data received. All information received on serious adverse events are reviewed by 1 of 2 trained registered nurses prior to coding. Reports can be sent from hospitals treating the patient, the patients themselves, or the national registers. Reporting malignancies to the national cancer registries is mandatory by law in the UK. To allow serious adverse events to be processed, the following information is required as a minimum:

- A legible and recognised disorder/sign/symptom;
- The date of event;
- Which targeted therapy drug(s) the patient was on at the time of the event.

Where information is missing, the BSRBR-RA pharmacovigilance team contacts the hospital to validate and confirm the details around the serious adverse event. Where a serious adverse event is patient reported, a request for information is sent to the hospital for validation. Events that do not fall under the definition of a serious adverse event are not subject to such validation. The data undergo regular validation checks both manually and automatically.

9.9. Limitations of the Research Methods

This study is designed to assess the safety of Ruxience within the clinical practice setting utilising the BSRBR-RA, a well-established UK based rheumatology register.

The RA treatment landscape has evolved over time with the introduction of new therapies, treatment recommendations, and approaches to managing these events. The rates of events of interest and their distribution among patient types may have changed over time.

Endpoint misclassification is of particular concern within the observational setting due to less stringent monitoring relative to clinical trials. While the BSRBR-RA has an established system to identify and capture endpoint data, it is not feasible in such an observational study to verify all events via source documentation. It is also possible that some events will be missed as all reporting is done via the rheumatology departments. If rheumatologists are not aware of an event, they cannot report it and could result in underestimation of the incidence rate. For the serious events included in this analysis this is of low probability.

This study will continue for a period of 3 years after study start (assuming it is feasible to continue participation and that a sufficient number of Ruxience-treated patients can be enrolled). This period of time may not be sufficient to assess some events, particularly malignancies which may have a longer latency period. Another limitation is the absence of a control group which does not allow for the comparison of incidence rates among Ruxience exposed patients to patients exposed to other treatments. Conclusions may not be generalisable outside of the 3 year period since initiation of therapy.

9.10. Other Aspects

Not applicable.

10. PROTECTION OF HUMAN SUBJECTS

10.1. Patient Information

This study involves data that exist in anonymised structured format and contain no patient personal information.

10.2. Patient Consent

As this study involves anonymised structured data, which according to applicable legal requirements do not contain data subject to privacy laws, obtaining informed consent from patients by Pfizer is not required. The University of Manchester will obtain written informed consent from all patients prior to data collection.

10.3. Institutional Review Board (IRB)/Independent Ethics Committee (IEC)

There must be prospective approval of the study protocol, protocol amendments, and other relevant documents (eg, informed consent forms if applicable) from the relevant IRBs/IECs. All correspondence with the IRB/IEC must be retained. Copies of IRB/IEC approvals must be forwarded to Pfizer.

The analyses for the Ruxience PASS will be completed using fully anonymised data. The data will not contain any patient identification information (eg, name), except for a unique number assigned for the purpose of linking files.

The BSRBR-RA protocols are approved by the North West 5 Research Ethics Committee (REC 00/8/053 with most recent approval amendment (#27) approval date of 06 Dec 2018).

10.4. Ethical Conduct of the Study

The study will be conducted in accordance with legal and regulatory requirements, as well as with scientific purpose, value and rigor and follow generally accepted research practices described in Guidelines for Good Pharmacoepidemiology Practices (GPP) issued by the International Society for Pharmacoepidemiology (ISPE), EMA, European Network of Centres for Pharmacoepidemiology and Pharmacovigilance (ENCePP) Guide on Methodological Standards in Pharmacoepidemiology. See [ANNEX 2. ENCEPP CHECKLIST FOR STUDY PROTOCOLS](#).

11. MANAGEMENT AND REPORTING OF ADVERSE EVENTS/ADVERSE REACTIONS

This study involves data that exist as structured data by the time of study start or a combination of existing structured data and unstructured data, which will be converted to structured form during the implementation of the protocol solely by a computer using automated/algorithmic methods, such as natural language processing.

In these data sources, individual patient data are not retrieved or validated, and it is not possible to link (ie, identify a potential association between) a particular product and medical event for any individual. Thus, the minimum criteria for reporting an AE (ie, identifiable patient, identifiable reporter, a suspect product, and event) cannot be met.

12. PLANS FOR DISSEMINATING AND COMMUNICATING STUDY RESULTS

In the event of any prohibition or restriction imposed (eg, clinical hold) by an applicable competent authority in any area of the world, or if the investigator party responsible for collecting data from the participant is aware of any new information which might influence the evaluation of the benefits and risks of a Pfizer product, Pfizer should be informed immediately.

Annual reports will be prepared by BSRBR and shared with Pfizer. Analysis using linked register data through 3 years of follow up will be the basis for the study final report. Data may be used in regulatory communications external to the UK or for contextualisation purposes. Manuscripts based on specific endpoints of interest may be developed for publication purposes.

In the event of any prohibition or restriction imposed (eg, clinical hold) by an applicable Competent Authority in any area of the world, or if the investigator is aware of any new information which might influence the evaluation of the benefits and risks of a Pfizer product, Pfizer should be informed immediately.

In addition, the investigator will inform Pfizer immediately of any urgent safety measures taken by the investigator to protect the study patients against any immediate hazard, and of any serious breaches of this NI study protocol of which the investigator becomes aware.

14. LIST OF TABLES

Table 1. Precision Estimates for Reported Incidence Proportions of Safety Events in Ruxience RMP

Table 2. ICD and MedDRA Codes for Select Safety Endpoints

15. LIST OF FIGURES

Not applicable.

ANNEX 1. LIST OF STAND ALONE DOCUMENTS

Table 2. ICD and MedDRA Codes for Select Safety Endpoints

Event	ARTIS		BIOBADASER, BSRBR, RABBIT
	Operationalisation	Validation ICD	Operationalisation (Final list TBD based on reported endpoints)
Serious infections	Hospitalisations in the Patient Register listing as main diagnosis ICD10-codes below. If main diagnosis is RA, contributory diagnoses are also considered. A00-B99 (excluding A33 and A50), D73.3, E32.1, G00-G02, G04.2, G05-G07, H00.0, H44.0, H60.0-H60.3, H66-H67, H70, I30.1, I40.0, J00-J22, J32, J34.0, J36, J39.0-J39.1, J44.0, J85, J86, K04.4, K04.6, K04.7, K10.2, K11.3, K12.2, K14.0, K57.0, K57.2, K57.4, K57.8, K61, K63.0, K65.0, K65.1, K65.2, K65.9, L00-L08, L30.3, M00-M01, M46.2-M46.5, M60.0, M65.0, M71.0, M71.1, M72.6, M86, N13.6, N15.1, N15.9, N30.0 N30.8, N34.0, N41.2, N43.1, N45.2, N45.3, N45.4, N48.2, N61, N70, N73, N75.1.	This algorithm has not been specifically validated in ARTIS, but the register itself is subject to strict quality assurance routines and has been validated several times. References: Ludvigsson et al. External Review and Validation of the Swedish National Inpatient Register, BMC Public Health, 2011 (11):450. http://www.socialstyrelsen.se/register/halsodataregister/patientregistret/inenglish .	Hospitalisation and/or use of parenteral antibiotics + MedDRA Infections and Infestations SOC 10021881.
CV risk	Major Acute Cardiovascular Events (MACE), combines MI, stroke, and fatal cardiovascular events: I00-I99 as main cause of death, or I20.0, I21, I60-I64 as diagnosis in in- or outpatient care.	See Serious Infections ‘Outcome’ was defined as any first-ever acute coronary syndrome (ACS) event, which in turn was defined as a primary discharge diagnosis of acute myocardial infarction or unstable angina pectoris, or as acute myocardial infarction being the underlying cause of death. For discharge diagnoses, the date of admission to hospital was considered the event date. This outcome definition has	Fatal and non-fatal 10000891 Acute myocardial infarction; 10006147 Brain stem infarction; 10006148 Brain stem ischaemia; 10008034 Cerebellar infarction; 10008088 Cerebral artery embolism; 10008120 Cerebral ischaemia; 10008190 Cerebrovascular accident; 10014498 Embolic stroke; 10019005 Haemorrhagic cerebral infarction; 10019016 Haemorrhagic stroke; 10024033 Lateral medullary syndrome; 10028596 Myocardial infarction; 10028602 Myocardial necrosis; 10033697 Papillary muscle infarction; 10043647 Thrombotic stroke; 10049768 Silent myocardial infarction; 10051078 Lacunar infarction; 10055677 Haemorrhagic

090177e1953dcb50Approved\Approved On: 16-Oct-2020 13:28 (GMT)

Table 2. ICD and MedDRA Codes for Select Safety Endpoints

Event	ARTIS		BIOBADASER, BSRBR, RABBIT
	Operationalisation	Validation ICD	Operationalisation (Final list TBD based on reported endpoints)
		
previously been validated in a Swedish early RA cohort, with a positive predictive value of 95%. In addition, a regional validation study of hospitalised acute MI and stroke found positive predictive values of 96% and 94% respectively, in the period 1977 to 1987.
 
References: https://onlinelibrary.wiley.com/doi/epdf/10.1002/art.39267 Mantel et al. Risk Factors for the Rapid Increase in Risk of Acute Coronary Events in Patients With New-Onset Rheumatoid Arthritis. A Nested Case-Control Study. Arthritis & Rheumatology. 2015; 67(11):2845-2854.
 
Lindblad et al. Validity of register data on acute myocardial infarction and acute stroke. Scandinavian Journal of Public health 1993; 21 (1):3-9.
	
transformation stroke; 10056237 Migrainous infarction; 10059613 Stroke in evolution; 10060839 Embolic cerebral infarction; 10060840 Ischaemic cerebral infarction; 10061256 Ischaemic stroke; 10062573 Brain stem thrombosis; 10064961 Thalamic infarction; 10066591 Post procedural stroke; 10066592 Post procedural myocardial infarction; 10067167 Cerebellar embolism; 10067347 Thrombotic cerebral infarction; 10067462 Millard-Gubler syndrome; 10068621 Cerebellar ischaemia; 10068644 Brain stem stroke; 10069020 Basal ganglia infarction; 10070671 Cerebral septic infarct; 10070754 Inner ear infarction; 10071043 Basal ganglia stroke; 10071260 Carotid angioplasty; 10073945 Perinatal stroke; 10074422 Brain stem embolism.
 
Fatal only
 
10002886 Aortic aneurysm rupture; 10003173 Arterial rupture; 10003210 Arteriosclerosis; 10003212 Arteriosclerosis moenckeberg-type; 10006145 Brain stem haemorrhage; 10007522 Cardiac asthma; 10007554 Cardiac failure; 10007556 Cardiac failure acute; 10007558 Cardiac failure chronic; 10007559 Cardiac failure congestive; 10007559 Cardiac failure congestive; 10007560 Cardiac failure high output; 10007625 Cardiogenic shock; 10007684 Carotid arterial embolus; 10007686 Carotid artery aneurysm; 10007688 Carotid artery thrombosis; 10008023 Cerebellar artery thrombosis; 10008030 Cerebellar haemorrhage; 10008076 Cerebral aneurysm ruptured syphilitic; 10008086 Cerebral arteriovenous malformation haemorrhagic;

090177e1953dcb50\Approved\Approved On: 16-Oct-2020 13:28 (GMT)

Table 2. ICD and MedDRA Codes for Select Safety Endpoints

Event	ARTIS		BIOBADASER, BSRBR, RABBIT
	Operationalisation	Validation ICD	Operationalisation (Final list TBD based on reported endpoints)
			10008089 Cerebral artery occlusion; 10008092 Cerebral artery thrombosis; 10008111 Cerebral haemorrhage; 10008118 Cerebral infarction; 10008132 Cerebral thrombosis; 10018985 Haemorrhage intracranial; 10022758 Intracranial aneurysm; 10022840 Intraventricular haemorrhage; 10022841 Intraventricular haemorrhage neonatal; 10024119 Left ventricular failure; 10024242 Leriche syndrome; 10034476 Pericardial haemorrhage; 10036511 Precerebral artery occlusion; 10039163 Right ventricular failure; 10039330 Ruptured cerebral aneurysm; 10042316 Subarachnoid haemorrhage; 10042434 Sudden death; 10047279 Ventricle rupture; 10048380 Aneurysm ruptured; 10048761 Atrial rupture; 10049418 Sudden cardiac death; 10049993 Cardiac death; 10050403 Carotid artery dissection; 10051093 Cardiopulmonary failure; 10051328 Carotid aneurysm rupture; 10052019 Femoral artery occlusion; 10053633 Cerebellar artery occlusion; 10053649 Vascular rupture; 10053949 Vascular pseudoaneurysm ruptured; 10055803 Haemorrhage coronary artery; 10058178 Aortic occlusion; 10060874 Aortic rupture; 10060953 Ventricular failure; 10060964 Arterial haemorrhage; 10062585 Peripheral arterial occlusive disease; 10062599 Arterial occlusive disease; 10063081 Acute left ventricular failure; 10063082 Acute right ventricular failure ; 10063083 Chronic left ventricular failure; 10063084 Chronic right ventricular failure; 10064595 Haemorrhagic arteriovenous malformation; 10064601 Iliac artery occlusion; 10065441 Venous haemorrhage; 10065558 Aortic

090177e1953dcb50\Approved\Approved On: 16-Oct-2020 13:28 (GMT)

Table 2. ICD and MedDRA Codes for Select Safety Endpoints

Event	ARTIS		BIOBADASER, BSRBR, RABBIT
	Operationalisation	Validation ICD	Operationalisation (Final list TBD based on reported endpoints)
			arteriosclerosis; 10067057 Basal ganglia haemorrhage; 10067116 Carotid arteriosclerosis; 10068119 Aortic dissection rupture; 10068119 Aortic dissection rupture; 10068230 Cardiorenal syndrome; 10069694 Brachiocephalic artery occlusion; 10069695 Subclavian artery occlusion; 10069696 Coeliac artery occlusion; 10071716 Vertebral artery dissection; 10072043 Central nervous system haemorrhage; 10072789 Iliac artery rupture; 10073565 Intracranial artery dissection; 10073565 Intracranial artery dissection; 10073681 Epidural haemorrhage; 10075449 Brachiocephalic arteriosclerosis; 10076203 Radiation associated cardiac failure.
NMSC	Identified through the Cancer register as all malignancies with ICD-O/2 code C44, and all basal cell cancers recoded in the register's subcomponent on basal cell cancers Alt: all invasive NMSC, identified as non-benign ICD-O/2 code C44, and no basal cell cancers.	About 99% of cancers have been morphologically verified. Reporting of incident cancers (including invasive malignancies as well as cancer in situ) is mandatory and semi automated, resulting in an estimated coverage greater than 95%.	10004146 Basal cell carcinoma; 10004178 Basosquamous carcinoma; 10004179 Basosquamous carcinoma of skin; 10006059 Bowen's disease; 10007390 Carcinoma in situ of skin; 10064055 Lip squamous cell carcinoma; 10063693 Malignant neoplasm of eyelid; 10040808 Skin cancer; 10055115 Skin cancer metastatic 10041834 Squamous cell carcinoma of skin.
Malignancy	All invasive malignancies recorded in the cancer register, excluding NMSC.	See NMSC.	Malignant or unspecified tumours (SMQ).

090177e1953dcb50\Approved\Approved On: 16-Oct-2020 13:28 (GMT)

